Mobile or Web App (custom developed). *Review [guidance] and provide attestation of compliance*

Mobile or Web App (purchased). *Specify product and version:* | |

Online survey. *Specify mechanism/platform:* www.kobotoobox.org

3rd party collector (please specify): | |

Existing data shared with JHSPH by data provider via electronic access/transfer

Duplicate and backup copies will be secured with same rigor as original data

Other (please specify): | |

8. Devices/Platforms used for Analysis, Storage, Processing: Identify where the identifiable or de-identified data will be analyzed/stored. Check all that apply.

Pre-approved storage and analysis platforms managed by JH/JHSPH for which security and risk mitigation measures are known.

Identify pre-approved storage platform(s) being used:

JHM Preferred:

JH SAFE Desktop JH PMAP

Other Approved Platforms:

JH One Drive/JHSPH OneDrive JH IT-Managed Network Storage JHM/JHSPH Qualtrics

JHSPH HPCC JHSPH SharePoint JHSPH Shares JHU REDCap

MARCC-Secure Environment

Platform(s) not managed by JH/JHSPH, not pre-approved, and require a risk assessment review from JHSPH Data Security.

- Describe the not pre-approved platform(s) you plan to use: It is possible we may need to store data on separate commercial storage site so that it also can be accessed by colleagues in the field (often use JH OneDrive is not feasible due to poor connection and login issues with partners. If this is required, we will likely use the DropBox Platform because the Health Systems Program maintains a license and the study team is already using it.
- Describe the technologies you intend to use (software, hardware, connectivity) with a focus on the measures taken to secure collected data along the continuum of data collection, storage, transmittal and access: We plan to use Kobo Toolbox for data collection and transmission to a secure online server. Data is encrypted and this is an accepted platform used on widespread basis by our partner organizations.

9. Access to Data and Access Controls: How will you ensure that only authorized individuals can access the data? What access controls will you put into place to ensure that only authorized individuals may access and use the data. (For example, OneDrive [\[guidance\]](#) illustrates how to share files with “people you specify”. [\[JHSPH Shares\]](#) addresses providing permissions to individual people.) Check all that apply. Note: If you need assistance implementing secure access controls, contact [\[[contact]\]](mailto:[[contact]])

Will provide access to data in accordance with OneDrive/JHSPH-Shares guidance posted on JHU IT websites

Will use secure access controls to limit access to individual-level data

Will use secure access controls to provide other researchers controlled access only to aggregated study data

10. Data Sharing: Clarify if data are to be shared externally with third parties, including sponsors and other investigators, and whether only aggregated data will be shared, or if you will share individual-level data. Describe sharing and protection plans for that sharing, including the proposed use of data agreements.

Consider the following:

- *Information about your data sharing in the consent forms*
- *Information about data sharing laws in the country where data will be collected, and if they limit sharing, how you will comply with those limitations?*
- *Whether data will be shared in aggregate only, or individual level data*
- *Whether you plan to make the data publicly available, and in what form.*

Will not share data with outside investigators

Will make publicly available

Will share with restrictions/controls

Will share aggregated data only

Will share individual-level data without identifiers

Will deposit data into an existing data repository for future research. *Please explain:* | |

Future research use and data sharing will have limited purposes. *Please explain:* | |

Other sharing information: We believe that data must be made publicly available because this work is funded by USAID. Additionally, many open access journals require that de-identified data sets be published. We plan to publish deidentified data on [Humanitarian Data Exchange](#) at the end of the study.

11. Duration and Destruction: Explain how long data will be retained and the plan for eventual return, deidentification or destruction of data, including moving data to an archive.

We anticipate maintaining identifiable data for approximately 25-30 months, during study data collection and data verification/cleaning. After data cleaning is completed, all unique identifiers will be removed from the data and only a copy of de-identified data will be maintained. If GPS coordinates are maintained, a central cluster coordinate will be used instead of specific household locations.

A. Certificate of Confidentiality:

All NIH studies include Certificate of Confidentiality (C of C) protections with the grant; the consent form must include the C of C language provided in our template. Other funders may obtain C of C protections through NIH. [<https://grants.nih.gov/policy/humansubjects/coc.htm>]

Does the study have Certificate of Confidentiality protections? Yes No

VII. Risks of the Study:

A. Describe the risks, discomforts, and inconveniences associated with the study and its procedures, including physical, psychological, emotional, social, legal, or economic risks, and the risk of a breach of confidentiality. Include risks beyond individuals to include the study population as a group and community risks. Ensure that the risks described in the consent documents are consistent with the risks outlined in the research plan.

We do not anticipate any physical, psychological, emotional, social, legal, economic or breach of confidentiality risks to the study participants. The data being collected is not sensitive. The primary inconvenience for participants is time spent to participate in the study which is anticipated to be no more than two hours over the two year study period.

B. Describe steps you will take to mitigate or minimize each of the risks described above. Include a description of your efforts to arrange for care or referral for participants who may need it.

The JHU research team will ensure the data collection team receives training in privacy and confidentiality using content developed based on guidance from the JHSPH IRB. It is anticipated that data collectors will not have access to interview data after it has been transmitted from tablets and that only a small number of study teams will maintain access to the data, thereby reducing risk of breach of confidentiality.

C. Describe the anticipated frequency and severity of the harms associated with the risks identified above; for example, if you are performing "x" test/assessment, or dispensing "y" drug, how often do you expect an "anticipated" adverse reaction to occur in a study participant, and how severe do you expect that reaction to be?

Data will be collected two times, 24 months apart and involves only an interview and anthropometric measurement. We do not anticipate a significant chance of harm.

D. Describe the research burden for participants, including time, inconvenience, invasion of privacy in the home, out of pocket costs, etc.

We expect each round of data collection to require less than one hour for participants. There will be no out of pocket costs. Data will be collected at or near the respondent's home. The participant and interviewer will mutually agree on a private location, such that data collection can occur outside the home if invasion of privacy is a concern.

E. *Describe how participant privacy, and if relevant – family privacy - will be protected during data collection if sensitive questions are included in interviews, or if study visits occur in the home setting.*

The survey questionnaire will not include culturally and individually sensitive questions. The enumerator will secure a quiet place in or near the residence of each study participant to ensure privacy, and to ensure distancing from other family members and neighborhoods. The majority of information collected is focused on the household; individual information that is collected will be focused on care giver reports of child diet which is not sensitive.

F. *Levels of COVID-19 community transmission will vary considerably by geography and over time, and therefore, the responses to the pandemic may also vary. The risk of COVID-19 to study staff and participants from in-person research activities can be mitigated by appropriate study procedures. If you are conducting in-person research activities, please indicate the protections you plan to implement at your research site(s):*

- Not applicable
- COVID testing of staff
- COVID testing of study participants
- Indoor masking/wearing PPE
- Social distancing for indoor activities
- Symptom screening of staff
- Symptom screening of study participants
- Vaccination of research team members
- Other procedures/comments: we follow Ethiopian COVID guidelines

VIII. Direct Personal and Social Benefits:

A. *Describe any potential direct benefits the study offers to participants (“payment” for participation is not a direct personal benefit).*

All study participants benefit from the Ifaa project, however, there are no direct benefits to participating in this evaluation.

B. *Describe potential societal benefits likely to derive from the research, including value of knowledge learned.*

Findings from this study will contribute to an understanding of multi-sectoral development programming in Ethiopia. Knowledge learned will be applied by CRS in future programming and USAID in future funding calls for similar resilience programs.

IX. Payment or Token of Appreciation:

A. *Do you plan to provide a non-monetary token of appreciation (food, soap, tea, chlorine tablets, etc.) to study participants? If no payment is provided, the JHSPH IRB strongly encourages providing such tokens. If yes, please describe below.*

We do not plan to provide non-monetary tokens of appreciation due to the fact that households are receiving Ifaa benefits.

B. *If you plan to provide a monetary payment, describe the form, amount, and schedule of payment to participants. Reimbursement for travel or other expenses is not “payment,” and if the study will reimburse, explain.*

We do not plan to provide monetary payment due to the fact that households are receiving Ifaa benefits.

C. *Include the possible total remuneration and any consequences for not completing all phases of the research.*

Not applicable

X. Study Management:

A. **Oversight Plan:**

1. *Describe how the study will be implemented. List all parties, including collaborators and subcontractors, who will be “engaged” in the human subjects research project and their roles .*

The research will be led by a team from Johns Hopkins University (JHU) Department of International Health including [name], [name], and [name]. [name] will serve as the PI, [name] will lead on data quality monitoring and analysis, and [name], who is based in Ethiopia, will be responsible for training, data collection oversight and serve as the primary liaison between CRS and the data collection firm. The data collection firm will be jointly selected by CRS and JHU from a CRS list of pre-approved companies that have performed similar work for CRS previously. The data collection firm will be responsible for hiring enumerators which will have direct contact with study participants.

Prior to and during each phase of data collection, the team will have regular calls to ensure adequate coordination and progress; in addition regular data quality monitoring and email correspondence will be used as a means of communication during data collection. Following the training of survey teams, quantitative baseline data collection will be conducted at the participants' households using Tablets/smartphones on the KOBO data platform. The baseline survey planning and logistics, and participant recruitment and data collection is planned to occur in May 2023. Following the two years of Ifaa intervention, JHU endline data collection will occur in May 2025, and will follow a similar process as baseline.

A training protocol will be designed by the JHU study team which will be delivered over a several day period to data collectors prior to each round of data collection. The training will be led by [name] and supervisors from the local data collection firm. The training elements will include an overview of the study rationale, objectives, protocol, review of the quantitative tool, interviewing techniques, field survey procedures, field organization, quality control measures and IRB protocols, to ensure safety, confidentiality, and consent procedures. Training will include content based on the JHSPH IRB Field Guide and also be specifically tailored to the questionnaire content. As part of the training, a field test will be conducted to give enumerators the opportunity to practice the consent process and interviews; following the field test modifications may be made to further tailor the questionnaire to the context (during the baseline survey only).

At each round of data collection, enumerators will be directly supervised by a team leader with experience conducting surveys. Data collection will be co-supervised by the data collection firm (using their usual practices) with additional on-the-ground support from [name] along with remote data quality monitoring managed by [name].

2. *What are the qualifications of study personnel implementing the project?*

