June 12, 2023

Ifaa Effectiveness Evaluation on Food Security and Nutrition

NCT05825716

Clinicaltrials.gov NCT05825716

JHSPH IRB Research Plan for New Data Collection

IRB Version: 11May2023

For new data collection, new data collection plus secondary data analysis, biospecimen repositories, and data coordinating center protocols.

DO NOT DELETE ANY QUESTIONS FROM THIS TEMPLATE

PI Name: [name]

Study Title: Ifaa Effectiveness

IRB No.: 23765

PI Version No. / Date: Version 4, June 12, 2023

I. Aims of the Study:

The Ifaa Project is a USAID-funded Resilience and Food Security Activity (RFSA) that is being implemented by Catholic Relief Services (CRS) and partners in the East Hararghe Zone of the Oromia Region in Ethiopia. Ifaa targets households that are participating in Productive Safety Net Programme (PSNP) which is a social protection program administered by the Government of Ethiopia that provides food and cash assistance to vulnerable households. The Ifaa Project will deliver multi-sectoral programming in 241 kebeles (sub-districts) in nine woredas (districts) of East Hararghe Zone, however, intervention packages vary by location. The proposed effectiveness evaluation will quantify the impacts of three different intervention packages in terms of key project indicators in the areas of household food security, diet, and child nutrition.

II. Background and Rationale:

Food insecurity and child undernutrition are persistent challenges in Ethiopia. In early 2023, over 22 million Ethiopians are food insecure as a result of drought, conflict and rising food prices and the situation is expected to worsen.ⁱ Prevalence of chronic malnutrition (stunting) is estimated at 37% and prevalence of acute malnutrition (wasting) is 7% among children less than five years of age. Only 14% of children have adequate dietary diversity and 11% meet the criteria for having a minimally acceptable diet.ⁱⁱ

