As noted in Figure 1, the study includes three of the possible four Ifaa intervention combinations. Characterizing the impact of livelihoods programming without the Ifaa enhanced intervention was not considered a priority.

Figure 2. Study Flow Diagram

A longitudinal cohort design will be used to compare the effectiveness of three Ifaa intervention packages among PSNP beneficiaries: 1) the Ifaa basic package; 2) enhanced package without livelihoods; and 3) enhanced package with livelihoods. Under this approach, the enrolled households will have either a pregnant woman or children <36 months of age. Households will be followed over a two-year period, with the baseline and endline survey conducted at a similar time

³ Community led complementary feeding sessions (CCFLS) is a six month program targeted at children at risk of acute malnutrition or recently discharged from a malnutrition treatment program. It includes caregiver training on child feeding practices and growth monitoring and is a six month intervention, with intensive services/training in the first month and follow up monitoring.

period in the calendar year to avoid seasonal changes in food security. The magnitude of change in key indicators over time will be assessed for each group; if needed, adjusted models will be used to account for baseline differences between groups. Outcome measures of focus are aligned with Ifaa indicators and include measures of household food consumption and child diet. To ensure adequate geographic coverage, a **stratified sampling design** will be used as follows:

- (1) **Kebele Selection.** Two kebeles per intervention arm will be purposively selected in each of the nine woredas with the aims of 1) of maximizing geographic similarity in terms of agro-ecological zone (lowland, midland, highland) and remoteness; and 2) ensuring sufficiently large beneficiary population is available for sampling purposes. In the case of smaller kebeles where it appears unfeasible to attain three clusters, the sample may be distributed across additional kebeles within the woreda.⁴

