The outcome variables of focus at the household level will be measures of food security, including 1) [Food Consumption Score](#), 2) [Household Hunger Scale](#), and 3) [Coping Strategies Index](#). At the individual level, outcome variables of focus will include 1) [Infant and Young Child Feeding Indicators](#) (in particular achievement of minimum dietary diversity); and 2) prevalence of stunting and wasting, in accordance with the [World Health Organization Child Growth Standards](#). Background information on individual (e.g. literacy, age, pregnancy status) and household characteristics (e.g. size, residence location) will also be collected so that these can be controlled for or used for disaggregation in data analysis. All outcomes will be analyzed as continuous variables and as categorical variables based on pre-determined thresholds.

A descriptive analysis of household sociodemographic characteristics and outcome measures will be performed. Continuous variables will be presented as mean (SD) and categorical variables as n (%). ANOVA tests will be conducted for baseline characteristics and primary and secondary outcomes to examine the comparability between the three and intervention groups; individual/household characteristics with significant differences between groups at baseline will be controlled for in models that estimate the effect of the interventions.

The program effect on expected primary outcome measures will be estimated using mixed-effect linear regression analysis for continuous outcomes and Generalized Estimation Equation (GEE) model for binary outcomes. In the mixed-effects models, the random effect component included indicators to control for clustering at school levels. The fixed component included the intervention group (intervention vs. control), time and an interaction term for group and time. The GEE models will be used to examine binary outcomes with longitudinal data from both enrollment and endline. These models will estimate the change in a binary outcome among members of a given intervention group from enrollment to endline, compared to the change in the same outcome in the control. The GEE models also included an interaction term between the intervention group and time (baseline/endline).

5. **Answer the following if they are relevant to your study design:**

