A. *If the study has different arms, explain the process for assigning participants (intervention/control, case/control), including the sequence and timing of the assignment.*

The selected sites will be purposively allocated to 1) the Ifaa basic package (comparison); 2) basic package + care groups (intervention 1); and 3) basic package + care groups + livelihoods (intervention 2) by CRS and other implementation partners in ifaa project. The JHU research team is not engaged to the assigning interventions.

Sections B thru F are not relevant.

VI. Data Custody, Management, Security, and Confidentiality Protections:

1. Data Sources: Identify the source(s) of data.

Participant/Parent-Guardian/Legally Authorized Representative
 JHM Medical Records (from Epic)

Note for JHM Data Users Only: Please complete the **Data Trust Risk Tiers Calculator** available on the Applications and Forms page on the JHSPH IRB website: [<https://tinyurl.com/2p96md3s>] and upload a copy of the documents to the "Miscellaneous- Other" section of your PHIRST application.

In addition, review the **Data Protection Attestation for Research and/or Healthcare Operations** at: [<https://tinyurl.com/yszfkur>] and certify your attestation of compliance to those requirements.

I certify my attestation of compliance to JHM Data Protection Requirements

Non-JHM Medical Records
 Outside Data Provider (CMS, National Death Index, Insurance Co., etc.)
 Other Existing Records (please specify):
 |
 |

2. Data Content: Will you collect, use, and/or record personal identifiers about study participants for any purpose?

Please look at the list of identifiers in Question 3 to help answer this question. **Note: Limited Data Sets (including dates, ages, and zip codes) are considered to be "identifiable".**

Yes: Continue with Question 3

| | | |
|--|-------------------------------------|---|
|  | No: Skip to Question 6 | |
| 3. Data Identification: Identify the Personally Identifiable Information (PII)/Protected Health Information (PHI) you will access/collect by checking the box(es) below for "Recruitment" and "Study Data" needs. | | |
| Recruitment | Study Data | PII/PHI to be Accessed/Collected |
|  |  | Name, signature, initials or other identifiable code |
|  |  | Geographic identifier (address, GPS location, etc.) |

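### The aim promises the impact of three packages, but with Ifaa in every arm the design can estimate only differences in change between packages, and one of those is not listed

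*Combined protocol and SAP*

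**What the plan says.** - **Aim (Section I).** "The proposed effectiveness evaluation will quantify the impacts of three different intervention packages in terms of key project indicators".
- **Arms (III.A).** The packages compared are "1) the Ifaa basic package; 2) enhanced package without livelihoods; and 3) enhanced package with livelihoods". The item on assignment of arms (V.C, item 5.A) names Basic as the comparison. Section VIII.A confirms that "All study participants benefit from the Ifaa project". Table 1 shows that Basic is an active package that includes food aid.
- **Per-group change (III.A).** "The magnitude of change in key indicators over time will be assessed for each group". Section III.B bases the sample size on change within a group.
- **Setting (Section II).** "In early 2023, over 22 million Ethiopians are food insecure as a result of drought, conflict and rising food prices", and the text expects the situation to worsen. Surveys are planned for May 2023 and May 2025 (V.C).
- **Model (V.C.3).** "The fixed component included the intervention group (intervention vs. control), time and an interaction term for group and time". The binary-outcome model compares change in an intervention group with change in the control.
- **Allocation.** Section II says that assignment to Basic or Enhanced was random and that livelihoods kebeles were chosen on criteria set by the implementer. Section III.A says that half of the Basic kebeles get livelihoods at random. V.C item 5.A calls the allocation purposive. Section IV.A sets different planned participation for each arm.

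**The concern.** A package's impact is the difference between what happened with it and what would have happened without it. No arm shows the second quantity for Ifaa as a whole. For Basic there is no contrast at all. For the other two packages the only contrasts are with another Ifaa package.

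Within-arm change does not fill the gap. Surveying in the same season deals with seasonality, but not with drought, conflict or prices that differ between 2023 and 2025. If conditions ease, all three packages will look effective. If they deepen, all three will look ineffective or harmful.

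A second gap follows. The study keeps two Enhanced arms that differ in livelihoods programming, yet the analysis plan states contrasts only with control. The comparison between those two arms is left to be chosen after the data are in.

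**Working it through.** **1. What can be identified.** For arm g, write observed change as D(g) = P(g) + T, where P is the package effect and T an external trend common to the arms, on the scale of the model.

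- There are three observed changes: D(Basic), D(Enhanced) and D(Enhanced + Livelihoods).
- There are four unknowns: three package effects and T.
- D(Enhanced) − D(Basic) = P(Enhanced) − P(Basic), because T cancels. The same holds for the other two pairs, of which only two are independent.
- D(Basic) = P(Basic) + T cannot be split. A true 8-point benefit with an 8-point external worsening gives −8 + 8 = 0.

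If T differs between arms, the differences are biased too. That matters most for Livelihoods, where kebeles were chosen by criteria.

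**2. What the plan's sample size is for.** Inputs from III.B: power 80%, α = 0.05 (two-sided assumed), design effect 1.5, loss 20%. Treat baseline and endline as two independent samples and multiply by 1.5 × 1.2 = 1.8:

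- 34% to 26%: 514 × 1.8 = 925 (plan: 915).
- 48% to 40%: 604 × 1.8 = 1,087 (plan: 1,070).
- 19.5% to 27.5%: 440 × 1.8 = 792 (plan: 785).

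Eight of the nine rows of Table 3 agree within 3%. The exception is 34% to 24%: 581 against 609. The sizing is thus for one arm's before-after change, as III.B says.

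**3. How easily an external trend passes for a package effect.** Effective households per arm: 1,080 × 0.8 / 1.5 = 576. With no package effect and an external change δ from p0 to p1:

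SE = √{(1 − ρ)[p0(1 − p0) + p1(1 − p1)] / 576}; probability of significance = Φ(|δ|/SE − 1.96).

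Example, 34% to 29%, ρ = 0: SE = √[(0.2244 + 0.2059)/576] = 0.0273; 0.05/0.0273 − 1.96 = −0.13; Φ = 0.45.

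Over baselines of 34% and 48%, both directions, and ρ from 0 to 0.3:

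| Assumed external change | Probability that an arm's change is significant |
|---|---|
| 3 points | 0.17 to 0.26 |
| 5 points | 0.40 to 0.59 |
| 8 points | 0.78 to 0.94 |

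The values of δ and ρ are assumptions. The documents give neither.

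**4. What remains for the identifiable contrast.** Take no change in Basic and an 8-point change in Enhanced. Then SE = √{(1 − ρ)(V1 + V2)/576}, with V1 = 2p0(1 − p0) and V2 = p0(1 − p0) + p1(1 − p1).

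- From 34%, ρ = 0: √[(0.4488 + 0.4168)/576] = 0.0388; 0.08/0.0388 − 1.96 = 0.10; power 0.54. At ρ = 0.6 it is 0.90.
- From 48%: power 0.49 at ρ = 0 and 0.86 at ρ = 0.6.
- Detectable difference at 80% power: about 11 to 7 points from 34%, and 12 to 7 points from 48%.

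**The case against.** The strongest reply is that the plan already is comparative. Section III.A says it will compare packages, and V.C.3 estimates program effect through a group-by-time interaction, in which a common shock cancels. The sentence on per-group change goes on to mention adjustment for baseline differences between groups. Comparing active packages is a legitimate and disclosed choice. With group coded in three levels, Enhanced + Livelihoods versus Enhanced is simply the difference of two interaction terms. All of this stands. It means the planned model is sound for increments. It does not make the aim in Section I attainable, and it does not put the missing contrast on the list.

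Some stronger readings are tempting, but the documents do not support them:

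- A reader might infer that packages will be judged by their own change against Ifaa targets. Targets enter only as sample-size inputs, only one −10% row in Table 3 is marked as a target, and no analysis text defines success that way.
- A reader might take the gap between the 34% and 48% baselines as the size of external drift. Those figures differ in area, source and year, so they do not measure it.
- A reader might take it as known that the crisis lasts to May 2025. The text gives an early-2023 situation and an expectation. The argument needs only some external change over two years.
- A reader might say that comparing the two Enhanced arms isolates livelihoods. Criteria-based kebele selection and arm-specific eligibility stand in the way.

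**Conclusion.** The point holds as a mismatch between the aim and what the design can estimate. The impact of Basic and the absolute impact of any package cannot be estimated, and this does not depend on any numerical assumption. Within-arm change is package effect plus external trend. How misleading it would be depends on a trend that the protocol does not quantify, so the probabilities above are illustrations. They assume two-sided α = 0.05, the plan's own design effect and loss, and ρ of 0 to 0.3.

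It would be wrong to conclude that the planned effect model is invalid. It removes a shock common to the arms and can deliver increments. What it lacks is three-level coding and a stated contrast between the two Enhanced arms. Contrasts involving Livelihoods are open to selection and should not be presented as randomized. The participation criteria in IV.A also differ between Basic and Enhanced, so that contrast needs the same check on who is enrolled.

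**What to change.** - **Section I.** Restate the aim as estimating the difference in change in food security, diet and child nutrition for Enhanced over Basic, Enhanced + Livelihoods over Enhanced, and Enhanced + Livelihoods over Basic.
- **Section III.A.** State that within-arm change is descriptive and will not be reported as package impact, and that the impact of Basic is not estimated.
- **Section V.C.3.** Code group with three levels and list the three contrasts of group by time.
- **Livelihoods.** Describe both contrasts that involve it as non-randomized and subject to selection, citing the kebele criteria in Section II and the arm-specific eligibility in IV.A.
- **Allocation.** Reconcile the wording in Section II, III.A and V.C item 5.A.
- **Section III.B (helpful, not essential).** State what 1,080 households per group gives for these contrasts, with the assumed correlation.

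The cost is wording and a model contrast. No new data are needed. The real price is a narrower claim, with no absolute impact for any package, and it is best paid before endline.
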